4.1. Demographics and Baseline Characteristics

Table 2 presents a list of the demographic and baseline characteristics variables that will be summarized by treatment group and overall for the FAS (Section 2.2.2).

Table 2: Demographic and Baseline Characteristics Variables		
Continuous Variables:	Summary Type	
Age (years)	Descriptive statistics (N, mean, standard deviation [SD], median and range [minimum and maximum], and IQ range).	
Weight (kg)		
Height (cm)		
BMI (kg/m ²)		
UC Disease Duration (years)		
Mayo score		
Partial Mayo score		
Modified Mayo score		
Mayo subscores (rectal bleeding subscore, stool frequency subscore)		
CRP (mg/L)		
Fecal Calprotectin (mg/kg)		
Categorical Variables		Frequency distribution with the number and percentage of participants in each category.
Sex (male, female)		
Race ^a (American Indian or Alaska Native, Asian, Black or African American, Native Hawaiian or other Pacific Islander, White, Not Reported, Multiple)		
Ethnicity (Hispanic or Latino, not Hispanic or Latino, Not Reported)		
Region ^b (Eastern Europe, Latin America, Rest of World)		
UC Disease Duration (≤ 5 years, > 5 and ≤ 15 years, > 15 years)		
Mayo Endoscopy Subscore (moderate: subscore = 2, severe: subscore = 3)		
Extent of disease (limited, extensive)		
Severity of UC disease (moderately active: $6 \leq$ Mayo score ≤ 10 , severely active: Mayo score > 10)		
Abnormal CRP (> 3 mg/L)		
Abnormal fecal calprotectin (> 250 mg/kg)		
Tobacco use status (non-user, prior user, current user)		
(randomization stratification factor) Corticosteroid use (yes, no)		

^a If multiple race categories are indicated, the Race is recorded as 'Multiple'.

^b Eastern Europe: Poland, Russia, Ukraine; Latin America: Argentina, Mexico, Brazil; Rest of World: United States, Germany, Australia

4.2. Disposition Information

Participants who discontinued study intervention early, along with the reasons for discontinuation of study intervention (including those due to COVID-19 related events), will be summarized by treatment group and overall based on the FAS (Section 2.2.2). In addition, participants who terminated study participation early, along with the reasons for termination of study participation (including those due to COVID-19 related events), will be summarized by treatment group and overall based on the FAS.

A list of participants who discontinued study intervention early (including those due to COVID-19 related events) and a list of participants who terminated study participation early (including those due to COVID-19 related events) will also be provided.

4.3. Treatment Compliance

The number of participants receiving each scheduled study intervention will be summarized by treatment group for the FAS (Section 2.2.2). Compliance with randomized study intervention versus actual received study intervention will be presented in a summary table for the FAS.

In addition, a listing of participants who were assigned treatment but were never treated and a listing of participants who were unblinded during the study will be provided.

4.4. Extent of Exposure

The number and percentage of participants who receive study intervention will be summarized by treatment group for the Safety Analysis Set (Section 2.2.3). The cumulative dose of guselkumab and golimumab received will be summarized by treatment group based on the Safety Analysis Set.

In addition, the number of administrations of study intervention and average duration of follow-up in weeks will be summarized by treatment group for all participants in the Safety Analysis Set as part of the AE tables.

The distribution of participants by study intervention lot will also be summarized by treatment group for the Safety Analysis Set.

4.5. Protocol Deviations

Participants with a major protocol deviation will be summarized by treatment group based on the FAS (Section 2.2.2). Major protocol deviations will be categorized as study intervention administration deviations, study entry criteria not met, prohibited concomitant medications deviations, withdrawal criteria met but not withdrawn, or other (including a sub-category for COVID-19 related deviations).

In addition, participants who did not meet study entry criteria will be further summarized by category (UC disease criteria, Medication criteria, Laboratory criteria, Medical history criteria, and other) based on the FAS. Further, participants who had study intervention administration

deviations will be further summarized by category identified prior to unblinding (e.g., received wrong study intervention administration, missed study intervention administration, received study intervention administration outside of protocol specified window).

A listing of participants who had a major protocol deviation (including COVID-19 related deviations), a more detailed listing of participants who did not meet study entry criteria (by category), and a more detailed listing of participants who had a study intervention administration deviations will be provided. A listing of participants with minor protocol deviations related to COVID-19 will also be provided.

4.6. Prior and Concomitant Medications

Summaries of UC medication history (participants who took medications for UC and their length of exposure prior to the study), UC-related non-biologic medication history (ie, history of response to or intolerance of corticosteroids and immunomodulators [ie, 6-MP/AZA]), UC-related biologic medication history (ie, vedolizumab), and prior use of JAK inhibitors (ie, tofacitinib) will be provided by treatment group based on the FAS (Section 2.2.2).

UC-specific baseline medications (ie, 5-ASA and corticosteroids) will be summarized by treatment group based on the FAS. Baseline medications are defined as any therapy used at baseline prior to the first dose of study intervention.

UC-specific concomitant medications that are permitted and taken during the trial (i.e., oral 5-ASA and oral corticosteroids) will be summarized by treatment group based on the FAS. Concomitant medications are defined as any therapy used on or after the first dose of study intervention, including those that started before and are continued after the first dose of study intervention.

A listing of concomitant medications for COVID-19 infections will be provided.

5. EFFICACY

5.1. General Method of Analysis

Descriptive statistics (i.e., mean, median, SD, IQ range, minimum, and maximum) will be used to summarize continuous variables. Counts and percentages will be used to summarize categorical variables. Graphical data displays (e.g., line plots) may also be used to summarize the data.

Analyses suitable for categorical data (e.g., chi-square tests, Cochran-Mantel-Haenszel [CMH] chi-square tests, or logistic regression, as appropriate) will be used to compare the proportions of participants achieving selected endpoints (e.g., clinical response) in treatment groups. In cases of rare events, Fisher's exact test will be used for treatment comparisons. Continuous response parameters will be compared using a Mixed-Effect Model Repeated Measure (MMRM) model unless otherwise specified. If the normality assumption is in question, an appropriate transformation may be implemented before fitting the MMRM model. In cases of small sample size, t-test will be used for treatment comparisons.

5.2. Analysis Specifications

5.2.1. Level of Significance

A 2-sided significance level of 0.2 (equivalent to the 1-sided 0.1 level specified in the protocol) will be used for all hypothesis testing and no adjustments for multiple comparisons will be made. Nominal p-values will be presented.

5.3. Primary Efficacy Endpoint

The primary efficacy endpoint is clinical response at Week 12.

5.3.1. Definition

Clinical response: A decrease from baseline in the Mayo score (Section 5.3.1.1) $\geq 30\%$ and ≥ 3 points, with either a decrease in the rectal bleeding subscore (RBS) ≥ 1 or a RBS of 0 or 1.

5.3.1.1. Mayo Score, Partial Mayo Score, and Modified Mayo Score

The **Mayo score** was developed from the criteria of Truelove and Witts¹⁴ for mild, moderate, and severe UC and from the criteria of Baron et al² for grading endoscopic appearance. The Mayo score consists of the following 4 subscores:

- Stool frequency
- Rectal bleeding
- Findings of endoscopy
- Physician's global assessment (PGA)

Each subscore is rated on a scale from 0 to 3, indicating normal to severe activity, as defined in Attachment 1.

The **Mayo score** is calculated as the sum of the 4 subscores (stool frequency, rectal bleeding, PGA, and endoscopy findings) and ranges from 0 to 12 points. A score of 3 to 5 points indicates mildly active disease, a score of 6 to 10 points indicates moderately active disease, and a score of 11 to 12 points indicates severely active disease.

The **partial Mayo score**, which is the Mayo score without taking into account the findings of endoscopy, is calculated as the sum of stool frequency, rectal bleeding, and PGA subscores, and may take on values from 0 to 9.

The **modified Mayo score**, which is the Mayo score without the PGA subscore, is calculated as the sum of the stool frequency, rectal bleeding, and endoscopy subscores, and may take on values from 0 to 9.

Due to the requirement for endoscopy findings for the evaluation of the Mayo score, it is not feasible to evaluate the Mayo score at each scheduled visit in the study. Therefore, the Mayo score will be evaluated at Weeks 0, 12 and 38, and the partial Mayo score will be evaluated at the other

study visits. The modified Mayo score can be derived from the Mayo score and is not a separate evaluation.

Mayo Rectal Bleeding and Stool Frequency Subscores

The eCRFs capture seven days of rectal bleeding data and the number of stools per day prior to each visit at which the Mayo score or partial Mayo score is collected. Data from 3 of these 7 days are used to calculate the Mayo rectal bleeding and stool frequency subscores; sites are instructed to check the boxes next to the 3 days which are used (see [below](#) for information on what days the sites are instructed to use).

The Mayo rectal bleeding subscore is calculated as the average rectal bleeding number for the three days based on the criteria in Attachment 1.

The Mayo stool frequency subscore is calculated as follows: The absolute stool number is the average of the daily stool number over the three days. At the screening visit, each person indicates the number of stools he/she passed in a 24-hour period when in remission or before his/her UC diagnosis. The stool frequency subscore will be calculated based on the criteria in Attachment 1 by subtracting the number of stools when in remission or prior to UC from the absolute stool number.

Instructions on which 3 days to use in the calculation of the Mayo rectal bleeding and stool frequency subscores: Sites are directed to use the most recent 3 consecutive days within the 7 days prior to the visit and are directed to exclude the following:

- The day medications were taken for constipation, diarrhea or irregularity
- The day of a procedure or preparation for procedure (e.g. enema, other laxatives, or clear liquid diet) that would affect stool frequency and/or blood content of the stool
- The 48 hours after the use of antimotility agents (e.g. diphenoxylate hydrochloride with atropine sulfate or loperamide)
- The 48 hours immediately following a colonoscopy

If 3 consecutive days are not available, the sites are instructed to choose 2 consecutive days and the closest nonconsecutive day. If 2 consecutive days are not available, then 3 nonconsecutive days closest to the visit should be chosen. If 3 days (within the 7 days prior to the indicated visit) that meet the criteria defined above are not available, then the absolute stool number, stool frequency subscore, and rectal bleeding subscore cannot be calculated and will be missing in the eCRF.

Mayo Endoscopy Subscore

The endoscopic findings will be based on the criteria of the Mayo endoscopy subscore described in Attachment 1. The endoscopic findings will be assessed by the investigator (ie, local endoscopist) during the endoscopy procedure and by the central reader reviewing a video of the endoscopy. The endoscopy may be either a colonoscopy or sigmoidoscopy. A full colonoscopy will replace a sigmoidoscopy if screening for polyps or dysplasia is required. The central reader

will also perform a friability assessment (yes, no) for each endoscopy, except for those with an assessed endoscopy subscore of 0, which requires that no friability is present.

Participant eligibility at baseline will be based on the **final reported endoscopic subscore** as determined by the following process:

- If the local endoscopist and the central reader agree on the endoscopic subscore, the agreed score will be the **final reported endoscopic subscore**.
- If there is a discrepancy between the local endoscopist and the central reader scores, the video endoscopy will be submitted to a second central reader (designated for adjudication) who is blinded to the scores of the local and the first central reader. From the scores of the 3 readers (i.e., local reader, central reader, second central reader designated for adjudication), the score with which 2 readers agree will be reported as the **final reported endoscopic subscore**. If the scores of the 3 readers (ie, local reader, central reader, second central reader designated for adjudication) are all different, then the median score of the 3 scores will be the **final reported endoscopic subscore**.

Further details are provided in the imaging charter.

Unless otherwise specified, the analysis of endpoints that include the Mayo endoscopy subscore will be based on the final reported endoscopic subscore. If the final reported endoscopic score is not available, the corresponding central endoscopy score (central read 1) will be used, if available. If the central endoscopy score (central read 1) is also missing, then the local endoscopy score will be used, if available. If the local endoscopy score is not available, then the endoscopy subscore for the analysis will be left missing.

Mayo Physician's Global Assessment Subscore

The physician's global assessment acknowledges the 3 other Mayo subscores, the patient's recall of abdominal discomfort and general sense of well-being, and other observations, such as physical findings and the patient's performance status.

5.3.2. Primary Estimand (Estimand 1)

The primary estimand (Estimand 1), i.e. a precise definition of the primary targeted treatment effect, is defined by the following 5 attributes:

Treatment by Week 12:

Experimental:

- **Combination Therapy:** Guselkumab 200 mg IV q4w (Weeks 0, 4, 8) **AND** Golimumab 200 mg SC (Week 0) and 100 mg SC q4w (Weeks 2, 6, 10)

Controls:

- **Golimumab Monotherapy:** Golimumab 200 mg SC (Week 0) and 100 mg SC q4w (Weeks 2, 6, 10)

- **Guselkumab Monotherapy:** Guselkumab 200 mg IV q4w (Weeks 0, 4, 8)

Population:

Participants 18 -65 years old with moderately to severely active UC, as defined by a Mayo score of 6 to 12, inclusive, at baseline, including an endoscopy subscore ≥ 2 as obtained during the central review of the video endoscopy.

Variable (Endpoint):

Clinical response at Week 12 (Section 5.3.1). Participants who have intercurrent events in categories 1-3 (defined below) prior to Week 12 visit will be considered not to have achieved clinical response at Week 12.

Intercurrent Events and Corresponding Strategies:

The following are the intercurrent events (ICEs) for this study:

1. An ostomy or colectomy (partial or total)
2. A protocol-prohibited change in concomitant UC medication(s) (described in Attachment 2)
3. Discontinuation of study intervention due to lack of efficacy or due to an AE of worsening of UC
4. Discontinuation of study intervention due to COVID-19 related reasons (excluding COVID-19 infection)
5. Discontinuation of study intervention for reasons other than lack of efficacy or an AE of worsening of UC or COVID-19-related reasons (this would include COVID-19 infections)

ICEs in categories 1-3 will be handled with the **composite strategy**. ICE category 4 will be handled by the **hypothetical strategy** (as if participants would have not experienced this intercurrent event), and ICE category 5 will be handled by the **treatment policy strategy**. This estimand acknowledges that having an ICE in categories 1-3 is an unfavorable outcome. Participants experiencing ICEs 1-3 will be considered not to have achieved clinical response at Week 12. For participants experiencing ICE 4, data at all visits after an ICE will be set to missing. For participants experiencing ICE 5, their observed clinical response status at Week 12 (if available) will be used. For participants experiencing multiple ICEs, ICEs in categories 1-3 will override ICEs 4 and 5.

Population-level summary:

The difference in proportion of participants achieving clinical response at Week 12 between combination therapy and each monotherapy.

5.3.3. Analysis Methods for the Primary Estimand (Estimand 1)

5.3.3.1. Main Estimator (Analysis) for the Primary Estimand

The primary endpoint, defined in Section 5.3.1, will be analyzed based on the Primary Estimand (Section 5.3.2). After accounting for the ICEs for the primary estimand (Estimand 1), participants who are missing any or all of the Mayo subscores that comprise the primary endpoint at Week 12 will be considered not to be in clinical response at Week 12 (i.e. nonresponder imputation).

In the primary analysis, data from all participants in the FAS (Section 2.2.2) will be analyzed according to the randomized study intervention regardless of the study intervention they actually received. The treatment difference between combination therapy versus each monotherapy will be tested using a 2-sided CMH chi-square test stratified by corticosteroid use at baseline (yes, no) at the 0.2 significance level. The magnitude of the treatment difference will be estimated by the difference in the proportion of participants achieving clinical response at Week 12 between the combination therapy group and each monotherapy group with a 2-sided 80% confidence interval (CI) calculated based on Wald statistic.

The study will be considered positive if the combination therapy group is significantly different from both monotherapy groups at the 2-sided significance level of 0.2 for the primary endpoint.

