
Bowel Disease Questionnaire; IV=intravenous; PBMC= peripheral blood mononuclear cell; PK=pharmacokinetic; PGIC=Patient’s Global Impression of Change (of Severity of UC); PRO=patient-reported outcome; PROMIS=Patient-Reported Outcomes Measurement Information System; RNA=ribonucleic acid; SC=subcutaneous; TB=tuberculosis; UC=ulcerative colitis; W=Week.
 
a. Screening should occur within 8 weeks before the W0 visit. Visit dates are based on the participant’s original randomization date; visit windows are as follows: day of the scheduled visit ±4 days (ie, plus or minus 4 days).
 
b. All assessments are to be completed before study intervention administration, unless otherwise specified; PRO assessments should be completed first. At the screening visit, the C-SSRS should be completed as the first assessment after signing informed consent and before any other tests, procedures, or other consultations. When blood samples are to be collected for safety, PK, efficacy, and biomarkers evaluations at the same time point, the order of blood draws will be samples for CRP, hematology and chemistry, PK/immunogenicity, serum biomarkers, whole blood DNA (for those participating in the optional pharmacogenomic sub-study at Week 0), and whole blood RNA.
 
c. Participants who discontinue study intervention (but have not terminated study participation) before W12 visit should complete the W12 assessments at the time of discontinuation and a safety follow-up visit (see Table 2) approximately 16 weeks after their last study intervention administration.
 
d. Subjects who terminate their study participation before the W12 visit should complete the W12 assessments at the time of termination (which will serve as the early termination visit).
 
e. For participants who are receiving oral corticosteroids, the investigator must begin tapering the daily dose of corticosteroids at W6.
 
f. Participants randomized to combination therapy will receive guselkumab monotherapy after W12. Participants randomized to a monotherapy group will continue on their originally randomized monotherapy after W12.
 
g. Must be signed before first study-related activity.
 
h. The required source documentation to support meeting the enrollment criteria are noted in Appendix 6 [Section 10.6], Regulatory, Ethical, and Study Oversight Considerations. Check clinical status again before first dose of study intervention.
 
i. All participants will undergo QuantiFERON[®]-TB testing. If the QuantiFERON[®]-TB test is not approved/registered in the country in which this protocol is being conducted or the tuberculin skin test is mandated by local health authorities, a negative tuberculin skin test result (see Appendix 3 [Section 10.3]) is also required. In Ukraine, while the QuantiFERON[®]-TB test is not approved/registered, it is accepted, and a tuberculin skin test is not required.
 
j. Chest radiograph (posterior-anterior and lateral views, or per country regulations where applicable) must be obtained within 3 months before the W0 visit. Note: A chest CT scan is also acceptable in place of a chest radiograph.
 
k. Must be performed before any study intervention administration for female participants of childbearing potential.
 
l. Stool studies for enteric pathogens may be performed at either the central or local laboratory and must include a stool culture and Clostridium difficile toxin assay. These tests must be performed during screening or have been performed during the current episode of disease exacerbation (as long as the stool studies were performed within 4 months before the first administration of study intervention). Additional testing (eg, ova and parasites or Escherichia coli O157:H7
								

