2. GENERAL ANALYSIS DEFINITIONS

2.1. Visit Windows

Unless otherwise specified, actual scheduled visits will be used for over time summaries and listings with no visit windows applied.

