5.3.3.3. Sensitivity Analyses

For the primary estimand (Estimand 1), after accounting for the ICEs, the proportion of participants with missing clinical response status at Week 12 is expected to be quite small. Despite the expectation of a very small percentage of missing data at Week 12, the following sensitivity analysis will be performed using a tipping point analysis with exhaustive scenarios.

The following method will be utilized to vary the imputation of clinical response status at Week 12 for missing data after the intercurrent event rules have been applied. For participants with missing data at Week 12, the clinical response status will be imputed in an increasing manner by participant level for each study intervention. Specifically, for each participant, a responder/non-responder status will be imputed starting with the scenario where all participants are non-responders up to the scenario where all participants are responders. This would include all possible

scenarios of responder status for all missing data. For each scenario, an analysis same as described above in Section 5.3.3.1 for the primary analysis for the primary estimand will be performed.

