5.3.4. Supplementary Estimands

Two supplementary estimands (Estimands 2 and 3) are considered to support the primary estimand for the primary endpoint (Estimand 1).

5.3.4.1. Estimand 2

In this supplementary estimand for the primary endpoint (Estimand 2), all ICEs (Section 5.3.2) will be addressed by the **composite strategy**.

The attributes of this supplementary estimand are the same as those for the primary estimand (Estimand 1) with the exception of the Variable (Endpoint) and strategy for ICEs, which is described as follows:

Variable (Endpoint): Clinical response at Week 12. Participants who have any ICE in categories 1-5 (listed in Section 5.3.2) prior to the Week 12 visit will be considered not to have achieved clinical response at Week 12, regardless of the observed data.

5.3.4.2. Estimand 3

In this supplementary estimand for the primary endpoint (Estimand 3), all ICEs (Section 5.3.2) will be addressed by the **hypothetical strategy**.

The attributes of this supplementary estimand are the same as those for the primary estimand (Estimand 1) with the exception of the Variable (Endpoint) and strategy for ICEs, which is described as follows:

Variable (Endpoint): Clinical response at Week 12. Participants who have any ICE in categories 1-5 (listed in Section 5.3.2) prior to the Week 12 visit will be considered to have **missing** clinical response status at Week 12, regardless of the observed data.

This supplementary estimand uses a **hypothetical strategy** that considers the clinical response status at Week 12 after the ICE to be the same as for other participants in the same study intervention who had not yet experienced the ICE. The **hypothetical strategy** attempts to estimate the treatment effect if the randomized treatment is taken as specified in the protocol. As such, any clinical response status observed after an ICE is excluded in order to ensure results reflect participant experience on randomized treatment only. Therefore, utilizing the hypothetical estimand allows for an analysis of participants under the scenario when they are compliant with the investigative therapy, and thus, is justified clinically since it attempts to eliminate the potentially confounding effects due to ICEs.

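### Estimand 1 declares COVID-19 discontinuation (ICE 4) hypothetical, but the main analysis scores the resulting missing Week 12 data as non-response, and no planned analysis gives the declared estimate

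*SAP*

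**What the plan says.** SAP 5.3.2 (Estimand 1) lists five intercurrent events. ICEs 1-3 (ostomy or colectomy, prohibited UC medication change, stopping for lack of efficacy or worsening UC) are composite. ICE 4 (stopping for COVID-19 reasons other than infection) is hypothetical, "as if participants would have not experienced this intercurrent event". ICE 5 (stopping for any other reason) is treatment policy. The working rule for ICE 4 is: "For participants experiencing ICE 4, data at all visits after an ICE will be set to missing".

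SAP 5.3.3.1 gives the main analysis. Once the ICEs have been accounted for, "participants who are missing any or all of the Mayo subscores that comprise the primary endpoint at Week 12 will be considered not to be" responders. ICE 4 is not excepted.

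The surrounding analyses are:
- Sensitivity (SAP 5.3.3.3): "the following sensitivity analysis will be performed using a tipping point analysis with exhaustive scenarios", run over every responder/non-responder assignment of the missing cases.
- Estimand 2 (SAP 5.3.4.1): participants with "any ICE in categories 1-5 (listed in Section 5.3.2) prior to the Week 12 visit will be considered not to have achieved" response, so all five ICEs are composite.
- Estimand 3 (SAP 5.3.4.2 and 5.3.5.2): all five ICEs are hypothetical, with multiple imputation (MI) under missing at random.
- Remission: SAP 5.4.2 copies the Estimand 1 strategies, 5.4.3.1 uses non-responder imputation, and Estimand 6 uses MI with all ICEs hypothetical.

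Protocol 1.3, Table 1, bears on which data are missing. Participants who stop treatment before Week 12 "should complete the W12 assessments at the time of discontinuation" (footnote c), and those who leave the study "should complete the W12 assessments at the time of termination" (footnote d). Under SAP 2.1, "actual scheduled visits will be used for over time summaries and listings with no visit windows applied".

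**The concern.** A hypothetical strategy asks what the Week 12 outcome would have been without the COVID-19 disruption. Scoring non-response answers that only if every such participant would have failed on treatment. The SAP does not say so, and its planning response rates are 55% to 75%. The analysis labelled Estimand 1 would then report a COVID-19 stop as handled hypothetically while counting it as treatment failure.

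At stake is whether the reported primary difference is the effect that the SAP defines. The label is also easier to defend if it is settled before the Week 12 data are unblinded.

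**Working it through.** **Text check.** How each analysis treats the ICEs, for a participant whose Week 12 data are missing after ICE 4:

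| Analysis | ICE 1-3 | ICE 4 | ICE 5 |
|---|---|---|---|
| Estimand 1 as declared (5.3.2) | composite | hypothetical | treatment policy |
| Main analysis as written (5.3.3.1) | non-response | non-response | observed data |
| Estimand 2 | non-response | non-response | non-response |
| Estimand 3 | MI | MI | MI |
| Tipping point (5.3.3.3) | non-response | every possible status | observed data, or every possible status if missing |

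No row below the first matches it. The tipping-point analysis covers every value that the ICE 4 participants could take, but names no scenario as the estimate. The opening condition in 5.3.3.1 about accounting for the ICEs does not exempt ICE 4: 5.3.5.2 opens in the same way for Estimand 3, and there the statuses made missing by ICEs go on to be imputed.

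The same pairing of hypothetical strategy and non-response appears for remission (5.4.2 with 5.4.3.1) and for binary endpoints in 5.5.2/5.5.3 and 5.6.2/5.6.3. Continuous endpoints use MI or MMRM, which match.

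**Inputs.** SAP 1.4: 70 per arm, one-sided 0.1 per comparison, both comparisons required, response 75% for combination and 55% for each monotherapy. The number of ICE 4 cases is not given, so k cases per arm with missing Week 12 data is an assumption. By the April 2020 interim, 126 participants had completed Week 12 or left (SAP 1.2), leaving 210 - 126 = 84, about 28 per arm.

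**Reproducing the plan.** Exact enumeration of three binomials with z = (difference) / sqrt(p(1 - p) x 2/70), p pooled, rejecting above 1.2816, gives joint power 81.4%. SAP Table 1 states 81%. This is an unstratified approximation to the CMH test.

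**Balanced cases.** As planned, k participants are fixed non-responders and 70 - k are binomial, so the expected difference is 20 x (70 - k)/70 points. The hypothetical comparator drops the k participants (n = 70 - k), an approximation to imputation under missing at random.

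| k per arm | Difference as planned | Power as planned | Power, hypothetical |
|---|---|---|---|
| 0 | 20.0 | 81.4% | 81.4% |
| 1 | 19.7 | 80.1% | 80.8% |
| 2 | 19.4 | 78.9% | 80.2% |
| 3 | 19.1 | 77.7% | 79.7% |

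The tipping-point scenarios span 2k/70 for each comparison: 2.9, 5.7 and 8.6 points.

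**Uneven cases, 5 in total.**
- Three in combination, one in each other arm: 0.75 x 67/70 - 0.55 x 69/70 = 17.6 points, joint power 70.5%, against 81.2% under hypothetical handling.
- Three in guselkumab, one in each other arm: 0.75 x 69/70 - 0.55 x 67/70 = 21.3 points against guselkumab, joint power 82.8%.
- Each such split has probability C(70,3) x 70 x 70 / C(210,5) = 8.3% if the cases fall by chance.

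**Type I error, all arms at 55%.** Averaged over chance allocation of 5 cases, it is 10.2% per comparison and 3.3% joint, against 10.1% and 3.3% with no cases. Conditional on the guselkumab split, it is 13.5% for that comparison and 4.0% joint. Conditional on the combination split, it is 6.9% and 1.8%.

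**If assessments at discontinuation count as Week 12 data.** The status at discontinuation is then used. If response at that point is assumed to be half the Week 12 rate, power for k = 1, 2, 3 is 80.6, 79.9 and 79.2%.

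**The case against.** The strongest reply is that this is a label and little depends on it. Non-responder imputation agrees with protocol 9.4.1.2 for participants who do not return at Week 12. The SAP expects very few missing statuses. For response, the tipping-point analysis repeats the primary test under every outcome that an ICE 4 participant could have had. Estimands 3 and 6 already treat ICE 4 hypothetically by MI, for response and for remission.

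Most of this stands. It shows that the mismatch is unlikely to change the conclusion and that the primary test need not change. It does not supply the missing estimate: Estimands 3 and 6 also make ICEs 1-3 and 5 hypothetical, which is a different question, and remission has no tipping-point analysis.

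A reader might infer three stronger things that the documents do not support.
- That type I error is inflated. Treatment is blinded and the average error is essentially unchanged. The 13.5% figure holds only given one particular split of an assumed 5 cases, and the opposite imbalance lowers the error.
- That every ICE 4 participant is counted as a failure. This depends on whether the assessments requested at discontinuation or termination count as Week 12 data, which the SAP does not state.
- That non-responder imputation always works against the combination. It lowers the rate in whichever arm has the cases, so the difference can move either way.

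**Conclusion.** The point holds. As written, the main analysis does not estimate Estimand 1 for ICE 4 participants without Week 12 data, and no other planned analysis does. The defect is a mismatch between declared strategy and estimator, not an invalid test.

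The expected size is small: 0.7, 1.3 and 1.9 points of joint power for 1, 2 and 3 cases per arm, with an uneven split able to move the result in either direction. These figures rest on assumed ICE 4 counts, the planning rates of 75/55/55%, an unstratified test, and removal of cases as a stand-in for imputation under missing at random. It should be fixed because the correction is cheap and concerns the definition of the primary effect.

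**What to change.** Document the following before the Week 12 unblinding.

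1. Add, for response and remission, one analysis that matches the declared strategies. Impute Week 12 Mayo subscores only for ICE 4 participants, using the fully conditional specification model of SAP Table 3. Set ICEs 1-3 to non-response, keep observed data for ICE 5, score other missing data as non-response, and pool as in 5.3.5.2. This needs a newly specified imputation data set. Table 3 names only MIMayoData1, which was built for Estimand 3, where data for all five ICEs are set to missing.
2. Keep non-responder imputation as the primary test. State that for ICE 4 it is a failure-scoring rule and not the hypothetical estimate.
3. State whether Week 12 assessments done at discontinuation or termination (Schedule of Activities, Table 1, footnotes c and d) count as Week 12 data or as data after the ICE. This decides which ICE 4 participants are missing.

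An alternative to item 1 is to relabel ICE 4 as composite for binary endpoints. That changes the declared question to fit the estimator, after some sponsor personnel were unblinded to the interim data (SAP 1.5), and should be acknowledged as such. It would also change some primary scores if assessments at discontinuation count as Week 12 data, because composite handling overrides observed status.

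The cost of the main fix is one more pooled analysis per endpoint and a few sentences in the SAP. The primary test is not replaced; item 3 settles which data enter it.
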